5.5.4 Criteria for Defining the Severity of an Adverse Event

The AE grades will be based on NCI-CTCAE [Japan Clinical Oncology Group (JCOG), 2011]. Items unspecified by these criteria will be assessed according to the following criteria and recorded.

- CONFIDENTIAL -

Grade	Assessment Criteria
Grade 1 (Mild)	Mild; asymptomatic or mild symptoms; clinical or diagnostic observations only; intervention not indicated.
Grade 2 (Moderate)	Moderate; minimal, local or noninvasive intervention indicated; limiting age-appropriate instrumental ADL.
Grade 3 (Severe)	Severe or medically significant but not immediately life-threatening; hospitalization or prolongation of hospitalization indicated; disabling; limiting self care ADL.
Grade 4 (Life-threatening or incapacitating)	Life-threatening consequences; urgent intervention indicated.
Grade 5 (Death)	Death related to AE.

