 - For continuous variables, descriptive statistics of change from baseline value will be summarized at each post-baseline visit using SI unit.
 - Shift-from-baseline table: Shift from baseline baseline to highest value up to Week 12 or during entire period, and baseline to lowest value up to Week 12 or during entire period, for all laboratory variables. If the laboratory value of same subject is measured lower from normal range at one visit, and higher from normal range at the other visit, that subject will be counted as both low and high from baseline up to Week 12 or during entire period.

Laboratory Tests for NCI-CTC Toxicity Grading

Laboratory test results for the select laboratory tests will be graded programmatically using the standardized NCI-CTC toxicity grading criteria (Grade 0, 1, 2, 3, 4) specified in the 10.8 Appendix8 for this study. Shift-from-baseline to worst value up to Week 12 or during entire period will be provided. Note: AEs in this study are graded the investigator using NCI-CTAE Grade (1, 2, 3, 4, 5).

Laboratory Tests for Reference Range

Test results for the select laboratory tests in Table 7 will be summarized against the reference range indicated. Number and percentage for the Highest/Lowest values of each subject included in pre-specified reference range for select laboratory up to Week 12 or during entire period will be provided.

Table 7. Select Laboratory Variables and Corresponding Reference Ranges

Select Laboratory Variable	Reference Range	Highest/Lowest
Aspartate Aminotransferase (AST)	$\geq 1 \times \text{ULN}$ to $< 2 \times \text{ULN}$ $\geq 2 \times \text{ULN}$ to $< 3 \times \text{ULN}$ $\geq 3 \times \text{ULN}$	Highest
Alanine Aminotransferase (ALT)	$\geq 1 \times \text{ULN}$ to $< 2 \times \text{ULN}$ $\geq 2 \times \text{ULN}$ to $< 3 \times \text{ULN}$ $\geq 3 \times \text{ULN}$	Highest
Alkaline Phosphatase (ALP)	$> 2 \times \text{ULN}$ to $\leq 3 \times \text{ULN}$ $> 3 \times \text{ULN}$ to $\leq 5 \times \text{ULN}$ $> 5 \times \text{ULN}$	Highest
Total Bilirubin	$> 1.5 \times \text{ULN}$	Highest
Total Bilirubin	$\geq 1 \times \text{ULN}$ to $< 2 \times \text{ULN}$ $\geq 2 \times \text{ULN}$ to $< 3 \times \text{ULN}$ $\geq 3 \times \text{ULN}$	Highest
Low-Density Lipoprotein (LDL)	$> 160 \text{ mg/dL}$	Highest
Low-Density Lipoprotein (LDL)	$< 100 \text{ mg/dL}$ 100 to $< 130 \text{ mg/dL}$ 130 to $< 160 \text{ mg/dL}$ 160 to $< 190 \text{ mg/dL}$ $\geq 190 \text{ mg/dL}$	Highest

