Lymphocytes, Absolute Units	LYMP HAB	10 ³ /μL	Increase/ Lymphocyte count increased	Not applicable⁸		>4 - 20	>20		4.0	111	10 ³ /μL
Magnesium	MG	mg/dL	Increase/ Hypermagnesemia	WNL	>ULN - ≤3.0		>3.0 - ≤8.0	>8.0	4.0	115	mg/dL
Magnesium	MG	mg/dL	Decrease/ Hypomagnesemia	WNL	≥1.2 - <LLN	≥0.9 - <1.2	≥0.7 - <0.9	<0.7	4.0	117	mg/dL
Absolute Neutrophil Count	ANC	10 ³ /μL	Decrease/ Neutrophil count decreased	Not applicable⁸	Not applicable⁸	≥1.0 - <1.5	≥0.5 - <1.0	<0.5	4.0	112	10 ³ /μL
Phosphate (Phosphorus)	PHOS	mg/dL	Decrease/ Hypophosphatemia	WNL	Not applicable⁸	≥2.0 - <2.5	≥1.0 - <2.0	<1.0	4.0	117	mg/dL
Platelets	PLT	10 ³ /μL	Decrease/ Platelet count decreased	WNL	≥75.0 - <LLN	≥50.0 - <75.0	≥25.0 - <50.0	<25.0	4.0	112	10 ³ /μL
Potassium	K	mEQ/L	Increase/ Hyperkalemia	WNL	>ULN - ≤5.5	>5.5 - ≤6.0	>6.0 - ≤7.0	>7.0	4.0	115	mEQ/L ⁷
Potassium ⁴	K	mEQ/L	Decrease/ Hypokalemia	WNL		≥3.0 - <LLN	≥2.5 - <3.0	<2.5	4.0	117	mEQ/L ⁷
Urine Protein ⁵	UPROT		Increase/ Proteinuria	WNL	+	++	+++ or ++++		4.0	149	n/a
Sodium	NA	mEQ/L	Increase/ Hyponatremia	WNL	>ULN - ≤150	>150 - ≤155	>155 - ≤160	>160	4.0	116	mEQ/L ⁷

Sodium	NA	mEQ/L	Decrease/ Hyponatremia	WNL	≥130 - <LLN		≥120 - <130	<120	4.0	117	mEQ/L ⁷
Total Bilirubin	TBI LI	n/a	Increase/ Blood bilirubin increased	WNL	>ULN - ≤1.5×UL N	>1.5×U LN - ≤3.0×U LN	>3.0×U LN - ≤10.0× ULN	>10.0 ×ULN	4.0	107	n/a
Triglycerid es	TRI G	mg/dL	Increase/ Hypertriglyceri demia	WNL	> ULN ⁹ - ≤300	>300 - ≤500	>500 - ≤1000	>1000	4.0	116	mg/d L
Uric Acid ⁶	UAC ID	mg/dL	Increase/ Hyperuricemia	WNL			>ULN - 10	>10	4.0	116	mg/d L

¹ "n/a" is specified if the criteria are based strictly on a comparison of the value to its reference range.

² WNL = Within Normal Limits; LLN = Lower Limit of Normal; ULN = Upper Limit of Normal.

³ **Calcium Corrected** will be derived using the following formula: Calcium Corrected = $0.8 \times (4.0 - \text{Albumin}) + \text{Calcium}$, where 4.0 represents the average albumin level in g/dL, Albumin is measured in unit of g/dL, and Calcium is measured in unit of mg/dL.

⁴ Hypokalemia Grade 2 is the same as Grade1 but has additional clinical criteria that cannot be assessed. Therefore, it was decided to grade all criteria falling within $\geq 3.0 - < \text{LLN}$ as grade 2.

⁵ For Urine Protein, the maximum category is "++++", while NCI CTCAE version4.0 doesn't define "+++", "++++". So, these are defined as grade 3 per internal discussion.

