⁶ Hyperuricemia Grade 3 is the same as Grade1 but has additional clinical criteria that cannot be assessed. Therefore, it was decided to grade all criteria falling within $> \text{ULN} - 10$ mg/dL as grade 3.

⁷ For hyperkalemia, hypokalemia, hypernatremia and hyponatremia, the unit in the NCI reference is mmol/L, which has been converted to mEQ/L by multiplying 1.

⁸ For ANC, LYMPHAB, GFR, there are no reference range in central laboratory, so, NCI CTCAE grading scale is only defined for not-related reference range category. For PHOS, LLN=2.5mg/dL, while NCI Grade 1 is defined " $\geq 2.5 - < \text{LLN}$ ", so Grade 1 can't be defined.

⁹ For TRIG, the upper limit of normal range is 149 mg/dL. Therefore, WNL for Grade 0 is up to 149 mg/dL. But the lower limit of Grade 1 is originally more than 150 mg/dL. So, the definition for the lower limit of grade 1 is changed from 150 mg/dL to ULN.

- Hyperuricemia (see pg. 116 of NCI document) cannot be assessed accurately without knowing whether or not the subject was experiencing physiologic consequences, so it is not included in the table.
- Hemoglobinuria (see pg. 148 of NCI document) cannot be assessed accurately without knowing clinical or diagnostic observations, so it is not included in the table.
- Troponin T (see pg. 109 of NCI document) cannot be assessed accurately without knowing manufacturer ranges, so it is not included in the table.

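### SAP Appendix 9 contradicts itself on uric acid: Table 26 makes every value above ULN up to 10 mg/dL Grade 3, while a note below it says hyperuricemia is left out

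*SAP*

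**What the plan says.** Three statements in SAP Appendix 9 (section 10.9) bear on uric acid.

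- **Table 26** has a uric acid row, "Increase/ Hyperuricemia". Grade 0 is within normal limits, Grades 1 and 2 are blank, Grade 3 runs from above ULN to 10 mg/dL, and Grade 4 is above 10 mg/dL.
- **Footnote 6** states that "Hyperuricemia Grade 3 is the same as Grade1 but has additional clinical criteria that cannot be assessed" and that all values in the band are therefore graded as "mg/dL as grade 3".
- **The first note under the footnotes** says that hyperuricemia "cannot be assessed accurately without knowing whether or not the subject was experiencing physiologic consequences, so it is not included in the table".

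SAP 7.5.2 states how the table is used: "Laboratory test results for the select laboratory tests will be graded programmatically using the standardized NCI-CTC toxicity grading criteria". It adds: "Shift-from-baseline to worst value up to Week 12 or during entire period will be provided". Table 23 in Appendix 4 lists this output for placebo, 100 mg, 150 mg and reference up to Week 12, and for 100 mg, 150 mg and reference over the longer period. Uric acid is part of the biochemistry panel (Protocol 5.4.4), so values will exist to be graded.

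**The concern.** The row and the note give opposite instructions. A programmer who follows the row produces a uric acid toxicity shift table. One who follows the note produces none. Each could claim to comply with the SAP, so a planned safety output is left undetermined.

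If the row is followed, footnote 6 itself shows the difficulty. Grades 1 and 3 share one laboratory band and differ only by clinical criteria that the laboratory file does not hold, yet the whole band receives the higher grade. A subject without those clinical features appears two grades too high. SAP 7.5.1.1 describes Grade 3 as severe or medically significant when it grades adverse events, and readers are likely to carry that meaning over to a laboratory table. The longer-period table has no placebo column to show how common the label is without active treatment.

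**Working it through.** **1. Is the contradiction real?** The row is not an artefact of a broken table, because footnote 6 describes it in prose and explains the choice. The same list of notes also excludes hemoglobinuria and troponin T on the ground that they cannot be assessed accurately, and neither has a row in Table 26. The exclusion is carried out for two of the three tests and not for uric acid.

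**2. What does the row do?** Written as a rule, with u for uric acid in mg/dL:

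- u within normal limits: Grade 0
- ULN < u ≤ 10: Grade 3
- u > 10: Grade 4

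The documents give no uric acid ULN, so 6, 7 and 8 mg/dL were each assumed:

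| Assumed ULN | At ULN | ULN + 0.1 | 10.0 | 10.1 | Grades reachable from 1 to 15 mg/dL |
|---|---|---|---|---|---|
| 6 | 0 | 3 | 3 | 4 | 0, 3, 4 |
| 7 | 0 | 3 | 3 | 4 | 0, 3, 4 |
| 8 | 0 | 3 | 3 | 4 | 0, 3, 4 |

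Whichever ULN applies, Grades 1 and 2 cannot occur, and a value 0.1 mg/dL above normal is Grade 3.

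**3. How many subjects?** This cannot be computed, because the documents give no frequency of raised uric acid. For illustration only, let p be the share of subjects whose worst value lies in the Grade 3 band, and c the share of those who truly have the clinical consequences. In a group of n = 100 (the planned size of each study drug group, SAP section 4):

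- Shown as Grade 3 = n × p. With p = 2%: 100 × 0.02 = 2. With p = 20%: 100 × 0.20 = 20.
- Over-graded = n × p × (1 − c). Smallest case, p = 2% and c = 50%: 100 × 0.02 × 0.5 = 1. Largest case, p = 20% and c = 0: 100 × 0.20 × 1 = 20.
- Chance of at least one over-graded subject = 1 − [1 − p(1 − c)]^n. With p = 2% and c = 50%: 1 − 0.99^100 = 0.63. With p = 5% and c = 50%: 1 − 0.975^100 = 0.92.

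Expected counts double in the 200-subject reference group. Both p and c are assumptions. The illustration shows only that, at these frequencies, the table would probably contain such subjects.

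**4. Where does it reach?** Section 7.5.2 notes that adverse events are graded by the investigator, so the counts of TEAEs of Grade 3 or higher do not draw on Table 26. The same section plans no hypothesis tests on laboratory data. The effect is limited to the descriptive toxicity shift tables. A subject already in the band at baseline would appear as Grade 3 to Grade 3, which is no shift.

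**The case against.** The best defence is that this is a disclosed convention. Footnote 6 says that the higher grade was chosen deliberately. Footnote 4 does the same for hypokalemia, where a band shared by Grades 1 and 2 is reported as Grade 2. When laboratory data cannot separate two grades, taking the higher one is a defensible cautious rule. An unaffected view is also planned: raw values, change from baseline, and shifts to the highest and lowest value against the normal range.

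Much of this stands. It means that calling the band Grade 1 would be a debatable preference, not a correction. It does not remove the conflict with the note, since a convention cannot apply to a test that the SAP says is not in the table. The hypokalemia default moves one grade and stays below Grade 3, whereas the uric acid default moves two and reaches it.

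A reader might infer more than the documents support:

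- **That Grade 4 is also false.** Footnote 6 concerns only the band up to 10 mg/dL. Nothing suggests that grading values above 10 mg/dL as Grade 4 is wrong.
- **That the protocol itself defines these values as severe.** Protocol 5.5.4 does describe Grade 3 as "Severe or medically significant but not immediately life-threatening; hospitalization or prolongation of hospitalization indicated; disabling; limiting self care ADL". But that scale grades adverse events, and only those that NCI-CTCAE does not specify. Table 26 cites NCI-CTCAE for hyperuricemia.
- **That the default would mimic drug toxicity.** Protocol 1.3 reports higher creatinine and lower eGFR on ASP015K in RAJ1, but does not list uric acid among the laboratory changes. The rule is identical in every arm and at baseline, and relabelling the band would not change the ratio between arms in the share of subjects in it.

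**Conclusion.** The contradiction is established from the SAP's own text and needs no outside source. The consequence is conditional. If the row governs, subjects above ULN up to 10 mg/dL are shown as Grade 3 although the SAP says that the data cannot separate Grade 3 from Grade 1. If the note governs, no uric acid grade is produced.

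The point is modest. It concerns one analyte in descriptive laboratory tables, leaves the adverse event analyses alone, and by itself favours no arm. The number of subjects cannot be derived from the documents; the illustrative 1 to 20 over-graded per 100 rests wholly on the assumed frequencies. It is still more than a wording slip, because it decides whether a safety table shows Grade 3 results that its own footnote says the laboratory data cannot confirm. It should be settled, at almost no cost.

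**What to change.** Before unblinding, choose one of two repairs to Appendix 9.

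1. **Preferred:** delete the uric acid row and footnote 6, so that the table matches the note. Report uric acid through the planned summaries and the normal-range shift tables.
2. **If the row is kept:** delete the note, and label the band above ULN up to 10 mg/dL *Grade 1 or 3, not distinguishable* in place of Grade 3. The Grade 4 cell can stay.

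In the same edit, correct the cross-reference in section 7.5.2, which sends the reader to Appendix 8 for the grading criteria although they are in Appendix 9.

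The cost is a few lines of SAP text and a small programming change, with no new data. The downside is that the laboratory table will carry no single CTCAE grade for uric acid in that band. Symptomatic cases are still captured as investigator-graded adverse events. If the SAP has already been closed, section 1 requires the departure to be justified in the clinical study report.
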